6.1. Efficacy Evaluations

6.1.1. Lesion count

The Lesion Count is the total number of rosacea acne lesions (*i.e.*, papules, pustules and nodules) on the subject's face.

At Visits 1-7, the investigator will report the total number for each of the following lesion types on the face:

- Papules, defined as raised inflammatory lesions, <0.5cm in diameter with no visible purulent material
- Pustules, defined as raised inflammatory lesions, <0.5cm in diameter with visible purulent material
- Nodules, defined as any circumscribed, inflammatory mass ≥ 0.5 cm in diameter.

The investigator should count each lesion type separately papules first, then pustules then nodules. She/he should start counting at the middle of a subject's forehead moving clockwise ending where she/he started, then count the number of lesions on the nose and report the total number of lesions.

At Visit 1, to be enrolled and at Visit 2 to be randomized the subject must have a total of ≥ 10 and ≤ 40 inflammatory lesions (papules, pustules and nodules) with ≤ 2 nodules, on the face.

6.1.2. Investigator's global assessment (IGA)

The IGA is the investigator's assessment of the average overall severity of rosacea on the subject's face at a particular point in time. The investigator should NOT refer to any other assessments to assist with these assessments.

At Visits 1-7 the investigator will assess the rosacea on each subject's face and report the one integer that best describes the average overall severity using the scale below:

Investigator's Global Assessment	
Grade	Descriptor
0	Clear: No papules or pustules, no nodules, none or barely perceptible erythema
1	Near Clear: Very few (≤ 3) papules and/or pustules, no nodules, very mild erythema
2	Mild: Few papules and pustules present, no nodules, mild erythema
3	Moderate: Several papules and pustules are the predominant feature, ≤ 2 nodules may be present, moderate erythema
4	Severe: Numerous papules and pustules, multiple nodules may be present, severe erythema

At Visit 1, to be enrolled and at Visit 2, to be randomized, the subject must have an IGA grade of ≥ 3 (Moderate).

At Visit 2 the IGA must be completed prior to the start of the first study medication application.

6.2. Safety Evaluations

In addition to routine AE monitoring the following safety assessments will be performed.

6.2.1. Clinical laboratory sampling

At Visits 1 and 6 non-fasting blood samples for clinical laboratory analysis will be collected by a qualified staff member. At a minimum the following tests will be conducted:

Chemistry Panel	Complete Blood Count
Albumin	Hematocrit
Alkaline phosphatase	Hemoglobin
Alanine aminotransferase (ALT)	Platelet count
Aspartate aminotransferase (AST)	Red blood cell morphology
Blood urea nitrogen (BUN)	Red blood cell count
Bicarbonate	White blood cell count
Calcium	White blood cell differential
Chloride	% & absolute
Creatinine	Basophils
Glucose	Eosinophils
Lactate dehydrogenase (LDH)	Lymphocytes
Phosphorus	Monocytes
Potassium	Neutrophils
Sodium	
Total bilirubin	Complete Urinalysis
Total protein	
Uric acid	

The investigator or physician subinvestigator must review the results of each subject's Visit 1 clinical laboratory test results prior to Visit 2. The subject must be withdrawn from the study if any of the Visit 1 results are outside normal range for the laboratory AND, in the opinion of the reviewer, clinically relevant (CR).

The results of the clinical laboratory tests will be reported on the laboratory's standard reports. The investigator/subinvestigator must review all laboratory reports in a timely manner, noting NCR (not clinically relevant) or CR, or the equivalent, for any result that is outside the normal range for the laboratory then date and sign/initial the report.

The investigator/subinvestigator must report all laboratory results that are BOTH outside the normal range for the laboratory AND, in the opinion of the investigator/subinvestigator CR as medical history if found in the results for samples collected prior to the start of the first study medication application and as adverse events if found in the results for samples collected after the start of the first study medication application.

6.2.2. Local tolerability assessment (LTA)

The LTA is the investigator's assessment of the average overall severity of signs and the subject's assessment of the average overall severity of symptoms associated with irritation on the treated area. The investigator and subject must NOT refer to any other evaluation to assist with these assessments. This is not a comparison with the assessment at any other time point.

LTA Signs (assessed by the investigator):

- Erythema
- Scaling/dryness.

LTA symptoms (assessed by the subject):

- Stinging
- Burning
- Pruritus (itch).

At Visits 2-7, the investigator and the subject will evaluate the LTA signs and the LTA symptoms respectively.

The investigator will assess the LTA signs as follows:

- At Visit 2:
 - Prior to the first study medication application
 - 20 (\pm 4) minutes after the Application Completion Time.
- At Visits 3-7.

The subject will assess the LTA symptoms as follows:

- At Visit 2:
 - Prior to the first study medication application report the LTA for each symptom over the previous 24 hours
 - 10 (\pm 4) minutes after the Application Completion Time, report the LTA for each symptom since the Application Completion Time.
- At Visits 3-7:
 - Report the LTA for each symptom over the previous 24 hours.

The investigator, for the signs, should report the one integer that best describes the average overall severity on the face using the scales below:

Local Tolerability Assessment - Erythema	
Grade	Descriptor
0	Clear: No erythema present
1	Mild: Slight erythema
2	Moderate: Definite erythema
3	Severe: Marked, fiery erythema

Local Tolerability Assessment - Dryness/Scaling	
Grade	Descriptor
0	Clear: No signs of dryness or scaling
1	Mild: Slight roughness (may be more easily felt than seen), barely perceptible scaling
2	Moderate: Moderate roughness, definite scaling
3	Severe: Marked roughness, heavy scaling

The subject, for the symptoms, should report the one integer that best describes the average overall severity on the face using the scales below:

Local Tolerability Assessment - Stinging	
Grade	Descriptor
0	Clear: No stinging
1	Mild: Slight tingling, not bothersome
2	Moderate: Definite tingling, slightly bothersome
3	Severe: Intense stinging, bothersome and/or uncomfortable

Local Tolerability Assessment - Burning	
Grade	Descriptor
0	Clear: No burning
1	Mild: Slight warmth, not bothersome
2	Moderate: Definite warmth, slightly bothersome
3	Severe: Intense feeling of heat, bothersome and/or uncomfortable

Local Tolerability Assessment - Pruritus (Itching)	
Grade	Descriptor
0	Clear: No itching
1	Mild: Slight itching that is noticeable but is not bothersome
2	Moderate: Definite itching that is bothersome but does not disrupt activities or sleep
3	Severe: Intense itching this is bothersome and may disrupt activities or sleep

Follow these steps to complete the LTA for each symptom by a subject:

- An investigational center staff member, other than the evaluating investigator, will show the appropriate LTA symptom grading scale to the subject and instruct the subject on the time interval to be considered
- The staff member should not give any opinion on the meaning of the LTA descriptors
- The subject should verbally indicate the appropriate grade and the staff member will report the grade in the source document
- Both the subject and the staff member must initial and date the source document to indicate the subject performed the LTA for symptoms as instructed
- The staff member must not influence the subject's assessment.

6.2.3. Vital signs

At Visits 1, 2 and 7, a qualified investigational center staff member will measure the following vital signs:

- Body temperature
- Pulse rate
- Respiration rate
- Blood pressure (systolic and diastolic) after the subject sits quietly for at least 5 minutes
- Height (at Visit 1 only)
- Weight (at Visit 1 only).

A systolic blood pressure >140mm Hg or a diastolic blood pressure >90mm Hg is considered abnormal and therefore the investigator must define the reading as CR or NCR.

A weight of >300 pounds is considered abnormal and therefore the investigator must define the reading as CR or NCR.

Any measure that is, in the opinion of the investigator, abnormal AND CR must be recorded as history if found prior to the start of the first study medication application or as an AE if found after the start of the first study medication application.

6.2.4. Urine pregnancy tests

At Visits 1 and 7, the investigator or designee will perform a urine pregnancy test for subjects who are WOCBP. The urine pregnancy test kits used must have a minimum sensitivity of 25-mIU β -HCG/milliliter (mL) of urine.

Subjects who are WOCBP must have a negative pregnancy test result at Visit 1 to continue in the study.

If the result of any post-treatment urine pregnancy test is positive, the subject will be withdrawn from the study and the subject's pregnancy documented and followed.

6.3. Other Evaluations

6.3.1. Demographics

At Visit 1, the investigator or designee will interview each subject to obtain demographic information including date of birth, sex at birth, race and ethnicity.

6.3.2. Medical history

At Visit 1, the investigator or designee will record medical history information including all medical conditions and disease states that:

- Are ongoing
- Require concomitant therapy
- Are, in the opinion of the investigator, relevant to the subject's study participation.

For women who are not of childbearing potential the reason they are not of childbearing potential must be reported as medical history.

6.3.3. Standardized photography

At Visits 2-7, an appropriately trained investigational center staff member other than the evaluating investigator will take standardized photographs to document the status of rosacea on the subject's face. The study images are intended to be used for scientific, training and promotional purposes.

Care must be taken to ensure similar lighting, background, subject positioning relative to the camera and camera settings are used for each photograph.

Equipment, supplies, training and detailed instructions for obtaining and managing the photographs will be provided to the investigational center prior to the initiation of subject enrollment.

Study photographs are to document the status of the subjects' clinical condition.

7. ADVERSE EVENTS

Adverse events will be monitored throughout the study and reported to Accuitis, Inc. on the appropriate AE CRF.

7.1. Definitions

7.1.1. Adverse events (AE)

An AE is any untoward medical occurrence in a patient or clinical investigation subject administered a pharmaceutical product and which does not necessarily have a causal relationship with this treatment. An AE can therefore be any unfavorable and unintended sign or symptom associated with the use of an investigational product (including an abnormal laboratory finding), whether or not related to the investigational product.

Thus any new, clinically relevant worsening of an existing sign, symptom or disease, should be considered an AE.

Worsening of the Lesion Count, IGA or LTA should be reported as an AE only if the use of the study medication is interrupted or discontinued or other therapy is required to manage the event.

Every new episode or clinically relevant worsening of a chronic condition (*e.g.*, headaches, allergies, depression, and hypertension) should be reported as a separate AE, even if the condition is reported in the subject's medical history.

The investigator should, when certain, report a diagnosis rather than the signs, symptoms or clinically relevant abnormal laboratory values associated with the AE. Otherwise, signs, symptoms or abnormal laboratory values may be used to describe the AE.

An abnormality discovered (*e.g.*, clinically relevant laboratory abnormalities), prior to the first study medication application, should be reported as medical history, not as an AE.

7.1.2. Serious adverse event (SAE)

A Serious Adverse Event is any untoward medical occurrence that at any dose:

- Results in death
- Is life threatening
- Requires inpatient hospitalization or prolongation of existing hospitalization
- Results in persistent or significant disability/incapacity, or
- Is a congenital anomaly/birth defect
- Is an important medical event.

The term “life threatening” refers to an event in which the subject was at risk of death at the time of event; it does not refer to an event that hypothetically might have caused death if it was more severe.

Inpatient hospitalization is considered to have occurred if the subject is admitted to the hospital on an in-patient basis even if released the same day. Prolongation of hospitalization is defined as an additional night stay in the hospital. Hospitalization for a diagnostic test (even if related to an AE) or elective hospitalization that was planned before study enrollment are not themselves reasons for an event to be defined as a SAE.

Important medical events are those that may not be immediately life threatening, result in death, hospitalization but are clearly of major clinical significance and may jeopardize the subject or require intervention to prevent one of the outcomes listed in the definition above. These should also usually be considered serious. Examples of such events are intensive treatment in an emergency room or at home for allergic bronchospasm, blood dyscrasia or convulsions that do not result in hospitalization.

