7.2.2. Procedure for reporting a serious adverse event

Upon becoming aware of a SAE occurring during the AE reporting period, whether or not related to the study medications, the investigator must:

1. Take the appropriate medical action to ensure the subject’s safety
2. Immediately inform the Medical Monitor of the SAE by telephone:

[REDACTED]
Accutis, Inc.
Medical Monitor

3. Within 24-hours complete, as fully as possible, an AE CRF and an SAE form; fax or e-mail the forms and any other relevant information (*e.g.*, concomitant medication CRF, medical history CRF, laboratory test results) to the Accutis, Inc. Medical Monitor.
4. Monitor and document the progress of the SAE until it resolves or, if not resolved after the subject’s last study visit, until in the opinion of the investigator the AE reaches a clinically stable outcome with or without sequelae AND the investigator and Accutis, Inc. Medical Monitor agree that the SAE is satisfactorily resolved.
5. Inform the Accutis, Inc. Medical Monitor of SAE updates by telephone followed by an SAE form update sent by fax or by e-mail.
6. Comply with the appropriate regulatory requirements and Accutis, Inc. instructions regarding reporting of the SAE to the responsible IRB.

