**8.12.1. Adverse Events**

Verbatim terms for AEs reported during the study will be mapped to their corresponding thesaurus terms (preferred term and system organ class) from the Medical Dictionary for Regulatory Activities (MedDRA) coding dictionary, version 21.0. Summaries will be made

using the assigned preferred terms, and will be based on the number and percentage of subjects having at least one occurrence of the following:

- Any AE during the study;
- An AE within each system organ class;
- An individual AE (based on the preferred term).

Analysis will include frequencies and proportions of patients reporting AEs using the preferred terms and system organ class. Separate summaries of AEs with a suspected relationship to study medication (as reported by the Investigator) and by severity will be prepared. If applicable, the number of deaths and serious adverse events (SAEs) will also be presented, and events leading to discontinuation from the study will be listed and tabulated.

All AEs will be presented in a by-subject listing.

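### Protocol 7.1.2 exempts in-patient diagnostic admissions even when an on-study AE prompted them, so an AE serious only by such an admission is classed as non-serious

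*Protocol*

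**What the plan says.** Protocol 7.1.2 lists the criteria of seriousness. The hospitalization criterion reads "Requires inpatient hospitalization or prolongation of existing hospitalization" and names no purpose of admission. The explanatory paragraph adds that hospitalization is "considered to have occurred if the subject is admitted to the hospital on an in-patient basis even if released the same day".

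The same paragraph then sets two kinds of admission aside: "Hospitalization for a diagnostic test (even if related to an AE) or elective hospitalization that was planned before study enrollment are not themselves reasons". The sentence ends by saying that these "are not themselves reasons for an event to be defined as a SAE".

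Important medical events are a separate criterion in the same section, with the guidance "These should also usually be considered serious".

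Two later provisions depend on the classification. Protocol 7.2.2 sets out immediate telephone notice and 24-hour forms, and its trigger is "Upon becoming aware of a SAE occurring during the AE reporting period, whether or not related to the study medications". SAP 8.12.1 states that, if applicable, "the number of deaths and serious adverse events (SAEs) will also be presented". The SAP has no definition of seriousness of its own, so it takes over the protocol's.

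**The concern.** It is reasonable to exempt an admission arranged before the subject entered the trial, because such an admission says nothing about what happened on study. The parenthesis goes further. It covers a subject who develops a symptom or an abnormal laboratory value on treatment and is admitted in-patient for a test because of it. The general criterion would count that event as serious, and the exception removes it.

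Two things are at stake. One is timing: an event not classed as an SAE brings no immediate call to the Medical Monitor and no 24-hour form. The other is the safety summary: the event appears among non-serious AEs and not in the SAE count. Safety is part of the trial's main objective (Protocol 3). Two investigators could also classify the same case differently, depending on whether they describe the admission as being for the test or for the event.

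**Working it through.** The documents give no figure to reproduce, so the check sets the provisions side by side.

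1. **General rule (Protocol 7.1.2).** An untoward occurrence that requires in-patient hospitalization is serious. Any in-patient admission counts, even with same-day release. The purpose of the admission does not matter.

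2. **Exception (same paragraph).** An admission for a diagnostic test does not by itself make the event serious, and the parenthesis says this holds when the test relates to an AE.

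3. **Does the reference to planning before enrollment limit the diagnostic-test part?** Read naturally, it attaches only to elective hospitalization. Suppose that it governs both parts. Protocol 7.1.4 starts AE reporting at the first study medication (Visit 2), and Protocol 7.1.1 makes abnormalities found before then medical history. Enrollment is at Visit 1. An admission related to an AE would therefore ordinarily not have been planned before enrollment, and the parenthesis would have almost nothing to apply to. That reading does not readily remove the problem.

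4. **What happens to each kind of event under the present text?**
   - AE that requires in-patient care for the event itself: serious under the general rule; 7.2.2 applies and it is in the SAE count.
   - AE with an in-patient admission for a diagnostic test that also meets another criterion (death, life threat, disability, congenital anomaly, important medical event): serious under that other criterion; 7.2.2 applies and it is in the SAE count.
   - AE whose only serious feature is an in-patient admission for a diagnostic test: non-serious under the exception; 7.2.2 does not apply and it is not in the SAE count.
   - Elective admission planned before enrollment: not itself a reason for seriousness. This is not in dispute.

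5. **What is kept in the third case?** Protocol 7.2.1 requires every AE in the reporting period to be entered in the source documents and on the AE case report form. SAP 8.12.1 tabulates AEs by system organ class, preferred term, severity and relationship, and lists them all by subject. The record survives. The serious classification and the expedited report do not.

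6. **Size.** Neither document gives a rate of hospitalization, of diagnostic admissions or of SAEs. The number of events in the third case cannot be derived.

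**The case against.** The strongest reply is that this is drafting by rule and exception. One paragraph states when an admission has occurred and then names two admissions that do not by themselves confer seriousness. The later, specific sentence qualifies the earlier one, and an investigator who reads the whole paragraph gets an answer. This stands: a reader might infer a flat contradiction, but the text is an express exception whose scope is too wide.

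Second, the exception sets aside only the admission as a reason and leaves every other criterion open. This also stands, and it confines the point to events that are serious by admission alone. The important-medical-event route is only a partial backstop, however. It asks for clear major clinical significance and rests on judgment, and at admission for a test the significance may not yet be known. The admission criterion needs no such judgment.

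Third, the exception covers admission for a test, not any admission for work-up that includes observation or treatment. That is right as a matter of wording. In practice an admission for an unexplained event may serve several purposes, and the protocol gives no rule for choosing among them.

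Fourth, the trial enrolls about 36 subjects in good general health who use a topical ointment for 12 weeks, so such admissions may be few. The documents neither support nor exclude this.

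**Conclusion.** The point holds in a narrow form. The parenthesis in Protocol 7.1.2 brings AE-prompted in-patient diagnostic admissions into an exception, although the section's own criterion would otherwise count them. An AE that is serious only by such an admission is classed as non-serious, without expedited notice and outside the SAE count.

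Two stronger readings are not supported. A reader might infer that serious events disappear from the safety data. They do not, because the AE is still recorded, tabulated and listed, and it is an SAE if any other criterion is met. A reader might also try to size the problem from the planned 24 active subjects, where moving one event into the SAE count changes the result from 0/24 to 1/24 (1 ÷ 24 = 4.2%). That shows only how sensitive a small arm is to any single event. It does not show how often this one would occur.

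The conclusion assumes that investigators apply the exception as written and that the SAP's SAE count follows the protocol's classification. It does not depend on any event rate. It is an inexpensive improvement to safety reporting and not a threat to the efficacy analysis.

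**What to change.** Reconcile the sentences in Protocol 7.1.2. Delete the parenthesis that extends the diagnostic-test exception to AE-related admissions. Limit the exception to hospitalizations planned before enrollment and to diagnostic admissions not prompted by an AE. Every AE-prompted in-patient admission then follows Protocol 7.2.2 and enters the SAE count. SAP 8.12.1 needs no change, because it takes the protocol's classification.

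The cost is a short wording change in a protocol amendment and possibly a few additional SAE reports, some of which may turn out to concern minor events.

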7.1.3. Unexpected adverse event

An unexpected AE is any AE that the investigator defines as related to a study medication, the nature of which is not consistent with the Investigator’s Brochure or package insert.

